3 OBJECTIVES

3.1 Primary objective

The primary objective of this trial is to evaluate the efficacy of early corticotherapy + RAS blockade (versus RAS blockade alone) after 2 years of evolution in IgAN patients with severe histological lesions.

3.2 Secondary objectives

The secondary objectives are:

- to evaluate the efficacy of early corticotherapy + RAS blockade (versus RAS blockade alone) at 6 and 12 months of evolution

- to compare the evolution of histological lesions between treatment groups at 12 months

- to compare the evolution of measured GFR (mGFR) between treatment groups at 12 and 24 months (or estimated GFR (eGFR) if unavailable)

- to compare the evolution of proteinuria in each group

- to compare the quality of life in each therapeutic group
- to assess the tolerance of treatment of each therapeutic group
- to identify prognosis markers of failure at 24 months
- to assess the pharmacokinetics of corticosteroids in IgA nephropathy patients
- to assess the association between corticosteroid exposure and treatment failure
- to assess the association between corticosteroid exposure and genetic polymorphisms

- to assesse the association between genetic polymorphisms and treatment failure

3.3 Pharmacocinetic study

The pharmacokinetics of corticosteroids will be performed in the experimental group and in the control group in case of rescue treatment.

To assess the pharmacokinetics of methylprednisolone three blood samples (5ml/sample) will be done (i.e., one sample during each successive one-day hospitalization). The time delay between the drug infusion and blood draw sampling will be assigned according to the usual biolological exams planned during the hospitalization.

Then, two blood samples (5ml) for prednisone pharmacokinetic assessment at Month 2 (or after at least 8 days of rescue treatment) will be performed. These two blood samples will be taken within an interval of 2 hours without the imposition of a specific time frame. There must not be intake of prednisone within this interval of 2 hours. For the experimental group, one blood sample will be collected additionally at Month 4. Each dosage will require 5 ml of blood in heparin tube without separating gel. The dose of each drug, as well as the delay between the blood sampling and the administration of the drugs will be carefully recorded at each visit. All samples will be stored at -20°C on site and sent at the end of research by agreed transporter.

4 PLAN FOR THE RESEARCH

4.1 Concise description of the primary and secondary assessment criteria

For all endpoints, mGFR should be analysed at D0, M12 and M24, if available in the centre. If not, eGFR calculated according to CKD-EPI formula will be used.

4.1.1 Primary assessment criterion

The primary endpoint is the failure of treatment at 24 months, defined as:

- proteinuria/creatininuria ratio (PCR) > 0,5 g/g
- or mGFR < 80% of initial mGFR (or eGFR if unavailable)
- or loss of more than 10 ml/min/1,73m² of initial mGFR (or eGFR if unavailable)
- or end stage renal disease (ESRD)
- or renal transplantation
- or death.

4.1.2 Secondary assessment criteria

Failure at 6 months will be defined as:

- PCR > 0.75 g/g
- or PCR > 0.5 g/g and > 30% of initial PCR
- or eGFR < 80% of initial eGFR
- or ESRD
- or renal transplantation
- or death.

Failure at 12 months will be defined as:

- PCR > 0.75 g/g
- or PCR > 0.5 g/g and > 30% of initial PCR
- or mGFR < 80% of initial mGFR (or eGFR if unavailable)
- or ESRD
- or renal transplantation
- or death.

Histological lesions evolution at 12 months :

The evolution of histological lesions will be assessed as the proportion of patients of both therapeutic groups with persistent severe histological lesions in repeat kidney biopsy at 12 months.

GFR evolution (mGFR or eGFR if unavailable):

The evolution of GFR at 12 and 24 months will be assessed as:

- the absolute value of GFR
- the absolute difference of GFR from the baseline
- the annual degradation (ml/min/1,73m²/year) of GFR during the 24 months

Proteinuria evolution

The evolution of proteinuria will be assessed as:

- the absolute value of proteinuria at 12 and 24 months
- the absolute difference of proteinuria from baseline at 12 and 24 months

Identification of prognosis markers of failure at 24 months:

Clinical, histological, and biological data (including PCR ratio, eGFR and mGFR, renal histological lesions) will be compared between patients with or without failure.

Comparison of side effects in each therapeutic group.

Comparison of life quality scale in each therapeutic group with SF36 scale at 12 and 24 months

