2 SCIENTIFIC JUSTIFICATION FOR THE RESEARCH

2.1 Hypothesis for the research

In Immunoglobulin A (IgA) nephropathy, the deleterious prognosis of severe histological lesions can be improved with early corticosteroid therapy.

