Several retrospective studies have evaluated the response to therapy of specific histological lesions. Most of studies with appropriate statistical analyses demonstrated an interaction between therapy and histological lesions such as mesangial proliferation, endocapillary hypercellularity or cellular crescents. In a Japanese series of 35 patients treated with tonsillectomy and steroids for 12 months, crescents were present in 91% of the initial biopsies and 0% of the repeat biopsies at the end of treatment³⁵. A significant reduction in mesangial proliferation score between the first and second biopsies was also observed³⁵. Other studies showed a similar improvement of both mesangial proliferation and cellular crescents^{36,37} in patients treated with steroids. Interestingly, segmental glomerulosclerosis could also be reduced after treatment with steroids^{35,36}, suggesting segmental glomerulosclerosis in IgAN includes lesions with podocytopathy similar to FSGS responsive to steroids¹⁶. Similarly, tubulointerstitial fibrosis could be significantly decreased after steroids therapy³⁵, showing fibrosis is a dynamic process in IgAN and not only a scarring lesion.

Importantly, these histological responses have been retrospectively associated with an improvement of disease outcome by steroids. A small study of 28 patients demonstrated that necrosis within glomeruli and cellular crescents were associated with response to therapy (proteinuria and serum creatinine decrease after 3 months of steroid therapy)³⁸. In the Oxford classification cohort, patients with endocapillary hypercellularity had an improved outcome if they were treated with steroids^{12,13}. In a 702 Asiatic patient's cohort, the risk of incident ESRD decreased significantly by steroids treatment in patients with segmental glomerulosclerosis²². Finally, the VALIGA study, evaluating oxford criteria in 1147 European patients, demonstrated that the predictive value of each lesion was reduced in patients treatment in this serie.

Simultaneously, histological evaluation could also help identifying patients with no response to RAS blockade. Shi *et al* demonstrated in a serie of 294 patients that mesangial proliferation and tubulointerstitial fibrosis were predictive of persistent proteinuria after 3 months of RAS blockade: the presence of these lesions could then argue for the early use of corticosteroids²⁸.

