8 ASSESSMENT OF EFFICACY

Proteinuria/creatininuria ratio (PCR) and eGFR (CKD-EPI formula) evaluation

Serum creatinine will be evaluated with an enzymatic IDMS-traceable assay. Urinary protein, creatinine, sodium and urea will be evaluated on a 24-hour urinary collection (or urinary sample) at each visit.

Biochemistry analyses can be performed in private practice laboratories.

In case of failure, Proteinuria and eGFR will be re-evaluated on a second sample, within an interval of at least 14 days. For each visit, the final GFR and PCR value will be calculated from the second dosage.

Histological lesions evaluation

Renal biopsy will be performed and processed according to local practices. Histologic assessment will be performed according to the Oxford criteria studies. For patient inclusion, each inclusion criterium (mesangial proliferation, endocapillary proliferation, focal segmental glomerulosclerosis, tubular atrophy/interstitial fibrosis, cellular/fibrocellular crescents) will be scored by local pathologists. Secondarily, all renal biopsies will be re-evaluated *a posteriori* in the Necker pathology department.

Measured GFR evolution will be evaluated as follows:

mGFR will be performed according to local practice (iohexol clearance, inuline clearance, CrEDTA clearance, ...).

Given that the randomization is stratified by centre, the difference between the mGFR techniques should not have a major effect in data interpretation.

Identification of prognosis markers of failure at 24 months:

These factors will include (but are not restrited to):

- clinical factors (blood pressure, history of macroscopic haematuria, familial history of IgAN),
- biological factors (initial and time-average proteinuria, initial eGFR, time-average sodium chloride consumption),
- renal histological lesions evaluated *a posteriori* (oxford criteria, thrombotic microangiopathy, focal segmental glomerulosclerosis with features of podocytopathy)

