9.2 Description of statistical methods to be used

All statistical analyses will be performed by Dr [name] (Paris Centre Clinical Research Department) using R software (http://cran.r-project.org).

Primary analyses will include all patients who underwent randomization and will be conducted on the intention-to-treat principle for efficacy outcomes and according to treatment received for toxicity end points. A per protocol analysis will be also performed, after exclusion of the subjects with at least one significant protocol deviation.

Descriptive analyses will be done for the two arms of treatment. Continuous variables will be summarized as mean (standard deviation) or median [range] and categorical variables as frequencies and percentages.

Primary end-point

Percentages of patient with failure at 24 months (as defined earlier) will be compared between groups using Chi2 test. Treatment effect will be presented as Relative Risk (RR) and its 95% CI.

Secondary end-points

Secondary efficacy and safety end points were analysed using Chi2 test (or Fisher's test if appropriate) and Student t test (or Wilcoxon test if appropriate).

To explore the emergence of any time-related patterns of response to treatment, means and 95% confidence intervals (CIs) for changes relative to baseline in proteinuria and GFR were plotted vs time from randomization until end of follow-up at 24 months. Means and 95% CIs for changes from baseline were compared at 6, 12 and 24 months using Student t test. In addition linear marginal regression models will be performed, if appropriate.

Three subgroups analyses are planned to explore whether the primary outcome results differed in particular groups of patients. Histological subgroups will be defined as the presence of mesangial proliferation or not, the presence of endocapilary proliferation or not and the presence of cellular or fibrocellular crescents or not. Log binomial regression models will be used for the subgroup analyses and will include terms for treatment group, subgroup, and the interaction between treatment group and subgroup. The interaction terms represent potential subgroup differences in treatment effects.

For efficacy and safety comparisons, P values of less than 0.05 were considered to indicate statistical significance.

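### The search for prognostic markers of 24-month failure has no treatment term, so markers measured after randomisation are confounded with arm and a baseline marker that steroids neutralise shows about half its effect

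*Protocol*

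**What the plan says.** Section 3.2 lists the identification of prognosis markers of 24-month failure among the secondary objectives. Section 4.1.2 gives the method: clinical, histological and biological data "will be compared between patients with or without failure". Other items in that section (repeat-biopsy histology, side effects, quality of life) refer to the treatment groups. The marker item does not.

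Section 8 names the candidates. They include blood pressure, initial proteinuria and eGFR, time-average proteinuria, time-average salt intake, and "renal histological lesions evaluated *a posteriori* (oxford criteria, thrombotic microangiopathy, focal segmental glomerulosclerosis with features of podocytopathy").

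Section 9.2 gives two-group tests (Chi2 or Fisher, t or Wilcoxon) as the default for secondary efficacy and safety endpoints. It also states: "Three subgroups analyses are planned to explore whether the primary outcome results differed in particular groups of patients". Those log-binomial models "will include terms for treatment group, subgroup, and the interaction between treatment group and subgroup". They cover mesangial proliferation, endocapillary proliferation and crescents.

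On the premise, section 2.1 hypothesises that "the deleterious prognosis of severe histological lesions can be improved with early corticosteroid therapy". Section 2.3 says that most studies with appropriate analyses "demonstrated an interaction between therapy and histological lesions such as mesangial proliferation, endocapillary hypercellularity or cellular crescents", and that a large European validation cohort "demonstrated that the predictive value of each lesion was reduced in patients" who were treated (the end of that sentence is garbled).

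**The concern.** Half the patients are randomised to a treatment that is expected both to lower failure and to change the meaning of the lesions. A table of failures against non-failures that ignores arm then has two weaknesses.

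First, failures are mostly controls and non-failures mostly steroid-treated patients. Any marker that treatment itself shifts will differ between the two outcome groups, even if it says nothing about prognosis among patients treated alike. Section 2.2 reports that steroids reduce proteinuria, so time-average proteinuria is a realistic case.

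Second, if a lesion predicts failure under RAS blockade but not after early steroids, the comparison averages the two arms and understates the lesion's effect in controls. The three planned subgroup interactions address this for three lesions. They leave out segmental glomerulosclerosis and tubulointerstitial fibrosis, which are both inclusion lesions in section 6.1 and which section 2.3 says can regress on steroids. They also leave out thrombotic microangiopathy, podocytopathy features and every clinical and biological marker.

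**Working it through.** **Inputs from the protocol.** Failure 60% control and 35% experimental, 80% power, two-sided 5%, 61 per group (9.1); allocation 1:1 (4.2.1).

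**Assumed, because the protocol gives no figure.** Marker prevalence, marker effect in each arm, and the difference in a post-randomisation marker between arms.

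**1. The plan's own figure.** With p̄ = 0.475:

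n = [1.96·√(2·0.475·0.525) + 0.842·√(0.60·0.40 + 0.35·0.65)]² / 0.25² ≈ 61.4, so 62 per arm.

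The arcsine formula gives 61.3. At 61 per arm the power is 79.7%. The stated 61 is reproduced to rounding and this point does not affect it.

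**2. Mix of arms in the two outcome groups.**
- Failures: 0.60·61 + 0.35·61 = 36.6 + 21.35 = 57.95, of which controls 36.6/57.95 = 63%.
- Non-failures: 24.4 + 39.65 = 64.05, of which controls 24.4/64.05 = 38%.

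**3. Marker measured after randomisation, unrelated to failure within each arm.** With equal arms and marker prevalences qC and qE, pooled failure among carriers is (0.60·qC + 0.35·qE)/(qC + qE). Non-carriers follow in the same way.

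| Prevalence control/steroid | Pooled failure, carriers v non-carriers | Spurious difference | False-positive rate, pooled | Stratified by arm |
|---|---|---|---|---|
| 60/40 | 50% v 45% | 5 points | 9% | 5% |
| 70/30 | 52.5% v 42.5% | 10 points | 20% | 5% |
| 80/20 | 55% v 40% | 15 points | 40% | 5% |

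The rates come from 20,000 simulated trials with 61 per arm.

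**4. Baseline marker modified by steroids.** Randomisation makes prevalence equal in the arms on average, so the pooled risk difference is (RD control + RD steroid)/2. With prevalence 50%, control failure 75% v 45% and steroid failure 35% v 35%, the pooled rates are (75+35)/2 = 55% and (45+35)/2 = 40%. The difference is 15 points instead of 30, and the odds ratio is 1.83 instead of 3.67. Closed-form power is 38% pooled, 67% in controls alone and 42% for the interaction.

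The range over prevalence 30–70% and control risk difference 20–40 points is:

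| Neutralisation by steroids | Pooled power | Control-only power |
|---|---|---|
| Full | 17–60% | 30–91% |
| Half | 33–92% | 30–91% |
| None | 53–100% | 30–91% |

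Under full neutralisation the interaction test has 18–67% power.

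**5. Price of adding arm.** Simulated power at prevalence 50%, arm-stratified against pooled:
- full neutralisation (75/45, 35/35): 0.39 v 0.39
- half neutralisation (75/45, 42.5/27.5): 0.73 v 0.71
- shared effect (70/50, 45/25): 0.62 v 0.61

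Stratifying loses no power in any of these cases. It does not recover the halved effect in step 4, which needs the within-arm estimates.

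**The case against.** The best counter-argument is that section 4.1 is only a concise description. It says neither pooled nor unadjusted, the default tests of 9.2 are worded for efficacy and safety endpoints, and a statistical analysis plan that is not shown may add arm. That stands in part: pooling is the natural reading but an inference. What is stated, however, is a comparison by outcome alone, and this conflicts with the protocol's own premise.

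It is also fair that the three planned interactions cover exactly the lesion types named in the interaction sentence of section 2.3. The gap is confined to the remaining lesions and the other markers. Nor is the 63%/38% mix a bias for baseline markers, because randomisation makes them independent of arm. Most candidates named in section 8 are baseline measures, and only the time-averaged ones are clearly post-randomisation.

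A reader might infer that pooling erases the markers of interest. The documents do not support this. Full neutralisation halves the effect. Near-erasure (power about 0.08) needs a marker that reverses under steroids, such as 25% v 45%, and the protocol speaks only of reduced predictive value. At half neutralisation or less, pooling is about as good as a control-only analysis or better.

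A reader might also want to call a marker prognostic only on the control-arm estimate. For a shared effect (70/50, 45/25) that cuts power to 0.36 against 0.61 pooled. Under section 7.4.1 controls who fail early may also receive rescue steroids, so their estimates do not describe RAS blockade alone.

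**Conclusion.** The concern holds in a limited form. As written, the marker comparison ignores an arm effect of 25 points in planned failure. For markers measured after randomisation the consequence is confounding, with an illustrative false-positive rate of 9–40% against 5% when stratified. For baseline markers there is no confounding, only dilution. That dilution is a halving under full neutralisation and matters little when neutralisation is about half or less.

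All marker prevalences and effects here are assumptions, and the size of the problem depends on them. The omission touches one secondary objective and leaves the primary analysis and the sample size as they are. It is still worth correcting, because including arm loses no power in the cases examined and removes the confounding by arm shown above.

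**What to change.** - In sections 4.1.2 and 9.2, state that each candidate marker is analysed in a model for 24-month failure that includes randomised arm (log-binomial, as already planned for the subgroups). Make the arm-adjusted effect the main result. The plain table of failures against non-failures can stay as description.
- As exploratory output, report the effect within each arm and the arm-by-marker interaction, at least for segmental glomerulosclerosis and tubulointerstitial fibrosis.
- Identify which candidates are measured after randomisation.
- Do not reserve the word prognostic for the control-arm estimate. Describe control-arm estimates as RAS blockade with rescue steroids allowed.

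The change is to wording only and needs no new data. The downside is a few more low-powered exploratory estimates on about 58 expected failures. In the central case above, the interaction test has 42% power.

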4.2 Description of research methodology

4.2.1 Experimental plan

Phase III, prospective, multicenter, randomized open-labelled study.

Included patients will be randomized according to a 1:1 ratio:

- early corticotherapy + RAS blockade (experimental group)

or

- RAS blockade alone (control group), with corticosteroids in case of failure at 6, 9, 12 or 18 months or in case of rapid deterioration of renal function at 2 months and proposed corticosteroids in case of failure at 4 months.

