1 SUMMARY

Full title	Treatment of IGa nEphropathy according to Renal lesions
Acronym	TIGER
Coordinating Investigator	Pr [name] – Nephrology Department – Necker Hospital – 149
	[name]
Scientific Director	Dr [name] – Renal Transplantation and Nephrology
	Department - Henri Mondor Hospital - [name]
Sponsor	Assistance Publique – Hôpitaux de Paris
Scientific justification	Currently, IgAN treatment recommendations are only based on
	clinico-biological parameters. Steroids therapy appears to have
	a major role in IgAN treatment, but previous studies evaluating
	steroids lacked of optimal control group and reproducible
	evaluation criteria. No prospective study (including ongoing
	studies) with optimal RAS blockade had included renal
	pathology in patients selection criteria, although histological evaluation improves patients prognosis prediction. Until now,
	the lack of a reliable histological classification has precluded
	the use of histological lesions to evaluate IgAN prognosis and
	treatment. Given the recently identified major prognostic role of
	histological lesions in IgAN, we propose to introduce renal
	pathology to guide the treatment of IgAN in a multicenter study,
	using currently validated evaluation criteria of chronic kidney
	disease progression.
Primary objective and assessment	Primary objective
criterion	To evaluate the efficacy of early corticotherapy + RAS
	blockade (versus RAS blockade alone) after 2 years of evolution in IgAN patients with severe histological lesions
	Assessment criterion
	Failure at 24 months, defined as:
	Failure at 24 months, defined as: - proteinuria/creatininuria ratio (PCR) > 0,5 g/g
	 proteinuria/creatininuria ratio (PCR) > 0,5 g/g or mGFR < 80% of initial mGFR (or eGFR if unavailable)
	 proteinuria/creatininuria ratio (PCR) > 0,5 g/g or mGFR < 80% of initial mGFR (or eGFR if unavailable) or loss of more than 10 ml/min/1,73m² of initial mGFR
	 proteinuria/creatininuria ratio (PCR) > 0,5 g/g or mGFR < 80% of initial mGFR (or eGFR if unavailable) or loss of more than 10 ml/min/1,73m² of initial mGFR (or eGFR if unavailable)
	 proteinuria/creatininuria ratio (PCR) > 0,5 g/g or mGFR < 80% of initial mGFR (or eGFR if unavailable) or loss of more than 10 ml/min/1,73m² of initial mGFR (or eGFR if unavailable) or end stage renal disease (ESRD)

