	inflammatory dosages of acetylsalicylic acid m. Contraindication for RAS blockade therapy
	n. Known allergy or intolerance to corticoids or lactose
	o. Organ transplant patient
	The absence of measured GFR availability on the site is not an exclusion criterion.
Treatment being tested	3 IV pulses steroids followed by oral steroids for 4 months
Benchmark treatment	Renin angiotensin system blockade
Risks added by the research	B
Number of subjects chosen	122
Number of centres	27
Research period	Inclusion period : 24 months
	Participation period : 24 months+ 21 days max
	Total research period : 48 months
Number of inclusions expected per	0.3
centre and per month	
Funding source	French Health Ministery
Data Safety Monitoring Board	Non
anticipated	

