It should be noted that in most therapeutic studies of IgAN, renal function was evaluated with creatinine-based formula. However, it has been demonstrated that this type of evaluation criteria (such as doubling-serum creatinine or estimated GFR evolution) can overlook significative variations of renal function in chronic nephropathies^{23, 24}. In fact, when annual GFR loss is calculated by using estimated GFR (eGFR) (MDRD formula) or measured GFR (mGFR), GFR decline is similar between both methods in only 60% of cases²³. Other cases show difference between both methods of more than 2 ml/min/1,73m²/year (whereas mean GFR decline of IgAN with oxford criteria is approximately 5 ml/min/1,73m²/year) ^{12,13,23}. Then eGFR decline should be interpreted with caution in chronic nephropathies, including IgAN.

Nephroprotection

Treatments inhibiting the renin angiotensin system (RAS), with strict blood pressure and proteinuria goals, have a major role in limiting the progression of $IgAN^{25,26}$. In fact, in a Spanish study, RAS blockade allowed a reduction from 91% to 55% of proportion of patients with doubling serum creatinine after 7 years of follow-up²⁷. Current recommendations include blood pressure target < 130/80mmHg and proteinuria < 0,5g/d (as recently validated by the VALIGA study²¹). It should be noted that these recommendations were not reached in previous therapeutic studies^{25,26}. About 60% of patients do not respond to these therapies after 3 months of follow-up, according to a recent Asiatic serie²⁸. Then, expert opinion supports the use of corticosteroids in patients with progressive disease despite RAS inhibition^{25,26}, in a 2-step strategy (initial RAS inhibition, then corticosteroids therapy).

Corticosteroids

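### The summary, 3.1 and the first item of 3.2 name RAS blockade alone as comparator, but failing controls get the same steroid course, so the M24 intention-to-treat analysis compares early with deferred steroids

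*Protocol*

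**What the plan says.** Three places state the comparison without rescue:

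- The summary gives the primary contrast as early corticotherapy plus RAS "blockade (versus RAS blockade alone) after 2 years of evolution in IgAN patients with severe histological lesions". It lists the benchmark treatment only as "Renin angiotensin system blockade". The summary as shown does not mention rescue steroids.
- Section 3.1 sets the primary objective: "to evaluate the efficacy of early corticotherapy + RAS blockade (versus RAS blockade alone) after 2 years of evolution".
- The first item of section 3.2 repeats the contrast for the earlier time points: "to evaluate the efficacy of early corticotherapy + RAS blockade (versus RAS blockade alone) at 6 and 12 months of evolution".

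The operative sections describe a different control strategy:

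- Section 4.2.1: "RAS blockade alone (control group), with corticosteroids in case of failure at 6, 9, 12 or 18 months". The same item adds steroids for rapid deterioration at 2 months and proposes them for failure at 4 months.
- Section 7.4.1 sets the rules. At M2 the course should be given if eGFR is below 70% of its initial value. At M4 it could be given on failure. At M6, M9, M12 and M18 it should be given on failure. Failure here means PCR above 0.75 g/g, or PCR above 0.5 g/g and more than 30% of its initial value, or eGFR below 80% of initial. A second sample at least 14 days later comes before any steroid. The course is the experimental arm's own.
- Section 7.4.2 rules out a second steroid course, so experimental patients have no matching rescue.

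Section 4.1.1 opens: "The primary endpoint is the failure of treatment at 24 months, defined as". Its components are PCR, GFR, ESRD, transplantation and death. Receipt of rescue is not one of them. Section 9.2 analyses efficacy by intention to treat in all randomised patients.

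**The concern.** The stated objective is what readers use to interpret the result. Here it promises a comparison with patients treated by RAS blockade only, whereas the control arm is a strategy in which failure on RAS blockade leads to the tested steroid regimen. The M24 analysis counts patients by arm and by M24 status, whatever steroids they received on the way.

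A positive result is not endangered. A null one is open to misreading. Under the objective as worded, it would be taken to mean that steroids add nothing to RAS blockade, which is close to the question that section 2.2 says is still under discussion. The design can say only whether starting steroids early did better than holding them until failure.

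**Working it through.** **The plan's own figure.** Inputs from section 9.1: control failure 60%, experimental failure 35%, two-sided alpha 5%, power 80%; 1:1 allocation from section 4.2.1. With pooled variance and no continuity correction:

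n = [1.960 × √(2 × 0.475 × 0.525) + 0.842 × √(0.60 × 0.40 + 0.35 × 0.65)]² / 0.25²

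= (1.384 + 0.575)² / 0.0625 ≈ 61.4, that is 62 per group.

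The protocol states 61, at which power is 79.7%. The figure reproduces to within a patient. The point concerns which contrast is estimated, not this arithmetic.

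**Step 1: what each arm can receive before M24.**

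| | Experimental | Control |
|---|---|---|
| RAS blockade | all | all |
| Steroids at the start | all | none |
| Same course on failure at M2, M6, M9, M12, M18 | ruled out (7.4.2) | instructed (7.4.1) |
| Same course on failure at M4 | ruled out | optional |

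The control arm is RAS blockade, with steroids deferred and conditional on failure. Controls who never fail get none.

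**Step 2: how a rescued control is counted.** Take a control whose PCR at M6 is above 0.75 g/g and is confirmed on the second sample. Section 7.4.1 says the steroid course should be given. Suppose that at M24 the PCR is no higher than 0.5 g/g, GFR is at least 80% of initial with no more than 10 ml/min/1.73m² lost, and no ESRD, transplantation or death has occurred. Under 4.1.1 this patient is not a failure. Under 9.2 the patient stays in the control arm. The result is one success credited to an arm that the objective calls RAS blockade alone.

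**Step 3: whether the per-protocol analysis restores the stated contrast.** Section 9.2 excludes patients with a significant protocol deviation. Rescue given under 7.4.1 follows the protocol, so it is no ground for exclusion and the contrast stays the same.

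**Step 4: which time points are affected.** Take nominal visit dates, the shortest wait for the repeat sample (14 days, about 0.5 month) and a 4-month course. Rescue triggered at visit t then runs from t + 0.5 to t + 4.5 months:

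| Trigger | Start | End |
|---|---|---|
| M2 | 2.5 | 6.5 |
| M4 (optional) | 4.5 | 8.5 |
| M6 | 6.5 | 10.5 |
| M9 | 9.5 | 13.5 |
| M12 | 12.5 | 16.5 |
| M18 | 18.5 | 22.5 |

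- M24: on these dates every rescue course has ended before the primary assessment.
- M12: courses from M2, M4 and M6 have ended and one from M9 is still running, so the M12 failure comparison is also early against deferred.
- M6: only M2 and optional M4 rescue can come first, so this comparison is touched far less.

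**Step 5: what each result supports.** If steroids do nothing whenever given, the two arms have the same failure probability and the test keeps its size. A significant difference is valid evidence for early over deferred treatment. A non-significant one is compatible with steroids working in both arms, early in one and late in the other, and so does not speak to a comparator without steroids.

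**The case against.** The best defence is that the protocol explains its own shorthand. Section 4.2.1 attaches rescue to the control-group label in a single item, and 7.4.1 sets it out visit by visit. The hypothesis, the justification and the objective all speak of early steroids, and early has meaning only against later. Section 2.2 describes existing practice as RAS inhibition first and steroids afterwards, and the control arm matches it. No investigator would treat differently and no statistician would run a different test.

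Most of this stands, and it is why the point is minor. A reader might infer that rescue is hidden or that the design is unsound. The documents support neither: rescue is stated openly and the strategy comparison is coherent. The defence does not cure the objective, because its parenthesis names a comparator that the M24 analysis does not estimate. Someone who reads only the summary sees no rescue at all.

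It can also be said that a non-significant superiority test at this sample size could not prove that steroids add nothing, even without rescue. That is correct. The comparator wording adds a separate limit, however: an imprecise answer to the stated question differs from an answer to another question.

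**Conclusion.** The point holds as a minor wording fault in the summary (including the benchmark treatment), section 3.1 and the first item of section 3.2. The primary M24 comparison, and with the same limit the M12 failure comparison, is early steroids against RAS blockade with steroids deferred until failure. The other items of 3.2, such as histology, GFR and proteinuria, do not name this comparator and are not faulted. The conclusion rests only on the protocol's text and needs no assumption about how many controls are rescued.

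Two stronger readings are tempting and unsupported:

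- That the trial is underpowered because rescue lowers the control rate. Section 9.1 gives 60% as the failure rate expected in the control group. The plain reading is the group as treated under this protocol, rescue included. On that reading the sample size stands.
- That most controls will be rescued. Section 2.2 does say "About 60% of patients do not respond to these therapies after 3 months of follow-up", but this comes from another population and without a stated definition of response. Rescue here needs confirmation on a second sample, and RAS blockade is still being increased at visits under 7.2.2. The documents do not give the number of rescued controls.

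**What to change.** In the summary (primary objective, matching secondary objective and benchmark treatment), section 3.1 and the first item of section 3.2, name the comparator as RAS blockade with deferred rescue corticosteroids in case of failure. Word the trial's conclusions to match: a null result at M24 or M12 means that no benefit of early over deferred steroids was detected.

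Keep the rescue rules, the M24 endpoint, the Chi2 test, the intention-to-treat analysis and the 122 patients as they are. The cost is a few words in three places, with no change to visits, treatment, analysis or sample size.
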